1.1. List of Abbreviations

11. *Leucosia* (Leucosia) *leucostoma* (Fabricius) (Fig. 11)

10.1007/s00339-007-0333-2

1. *What is the primary purpose of the study?*

For more information, contact the Office of the Vice President for Research and the Office of the Vice President for Student Affairs.

[REDACTED]
[REDACTED]
[REDACTED]
[REDACTED]

2. Document Information

2.1. Purpose and Scope

The purpose of the trial is to evaluate the performance, comfort and ease of use of the New F&P Full face mask seal in the home environment.

2.4. Monitoring Arrangements

FPH will be conducting the study, and as such the persons listed above will be excluded from the group responsible for monitoring this study. A complete list of responsible staff will be provided under the delegation of authorities log. The study will be monitored once, at the time when all the results are available and a monitoring report will be generated and filed under the investigators' files. The

Principal Investigator will have access to all source documents needed to verify the entries to the Case Report Form (CRF) and other protocol related documents; provided that participant confidentiality is maintained in agreement with local regulations it will be the principal investigator's responsibility to inspect the CRF at regular intervals throughout the investigation, to verify the adherence to protocol and the completeness, consistency and accuracy of the data being entered on them.

The investigator's file will contain the protocol/amendments, financial disclosure form, CRFs and data clarification and query forms, Independent Review Board (IRB) approval with correspondence, informed consent, staff curriculum vitae and authorization forms, screening and enrolment logs, and other appropriate documents/correspondence as per International Conference on Harmonization (ICH) and Good Clinical Practice (GCP) and local regulations.

2.5. Data Management

Data obtained for this investigation will be stored in the controlled document system and electronically on secure servers, which are only accessible by Clinical Research staff and those persons identified on the delegation of authority. Any data which is not kept in this secure manner will be de-identified in accordance with HIPAA protocols. Data obtained for this investigation will be recorded in source documents and attached to the CRF for both the administration of the study and collection of participant data.

3. Investigator Information

5.1. Identification of the Medical Device

5.2. Device Risk Analysis and Management

Positive Airway Pressure (PAP) therapy via a nasal or oro-nasal mask is standard clinical practice for participants with OSA. The risks associated with this treatment are limited to the potential for slight discomfort associated with the use of a oro-nasal mask during sleep.

6. Justification for a Clinical Trial

6.1. Synopsis

This investigation is a prospective, randomized, non-blinded, cross-over study. The investigation is designed to evaluate the performance, comfort and ease of use of the F&P Full face mask Seal amongst OSA participants. The trial mask seal allocation will be randomized prior to the participant's first visit for the investigation.

This study will be conducted in accordance with ICH/GCP guidelines. No deviation from the protocol will be implanted without prior review and approval of the sponsor except where it may be necessary to eliminate an immediate hazard to a research participant. In such case, the deviation will be reported to the sponsor as soon as possible. In this trial the sponsor and the investigator are the same company however the Sponsor will not be the investigator. To ensure roles are clearly defined and kept independent there will be a delegation of authority log to clearly define each individuals tasks.

6.2. Literature Review

Obstructive Sleep Apnea (OSA) is a common sleep breathing disorder effecting around 3-7% of men and 2-5% of women in the general population¹ and is characterized by periodic collapse of the upper airway during sleep. The standard treatment for obstructive sleep apnea is nasal continuous positive airway pressure (CPAP), which consists of pressurized air applied to the nose and/or mouth via an interface. Despite the effectiveness of CPAP in abolishing upper airway obstruction, acceptance of and adherence with therapy has been sub-optimal². Reasons for the low compliance include nocturnal awakenings, incorrect therapeutic pressure and primarily discomfort due to mask poor interface fit. Poor interface fit can result in facial abrasion, leak causing fluctuations in therapeutic pressure and irritation of the eyes ^{3,4}.

6.3. Preclinical Testing

6.4. Previous Clinical Experience

6.5. Justification for Administration

Participants will remain on their usual PAP pressure throughout the duration of the study. Qualitative data will be collected from participants through questionnaires to evaluate acceptability, comfort, overall experience and the ease of use of the mask. These measures require testing on human participants for this clinical trial. Quantitative data (efficacy data from CPAP download) will also be collected for the duration of the study to ensure the study mask provides effective treatment and performs as participants stand care.

7. Objectives of the Clinical Investigation

7.1. Hypothesis

7.2. Objectives

Primary objective:

- To evaluate the performance, comfort and ease of use of the F&P Full Face mask seal in a home environment in regards to the participants' view of overall comfort, experience and satisfaction.

7.3. Population

Approximately 40-45 participants will be recruited for the trial by CTF.

7.5. Essential Requirements of the Relevant Directive

Essential requirements are not applicable since this study is being conducted in the USA only.

8. Clinical Investigation Design

8.1. Type of Investigation

This investigation is a prospective, randomized, single-blinded, cross-over study.

8.2. Controls

The Normal F&P mask seal (trial Seal B) will act as the control for this investigation. Data collected from this mask seal will be compared to the data gathered from the New F&P seal.

8.3. Bias

The two different F&P mask seals are blinded however they may be distinguishable, therefore there is a possibility that bias would occur. The order of the two masks issued to the participants will be randomized, limiting this bias.

8.4. End Points

8.4.1. Primary Outcomes

- The F&P mask seal is comfortable to use for the participant as measured by the custom questionnaires and recorded during the interviews.
- The mask is easy to use, accepted by the participant and provides adequate treatment for OSA during in-home use, measured via participant feedback and PAP data download (if applicable)

8.4.2. Secondary Outcomes

- Seal performance as measured by leak measurements/PAP data (if applicable).

8.5. Variables

8.6. Measurements

8.7. Equipment

8.8. Inclusion / Exclusion criteria

Inclusion Criteria:

- Adult (22+ years of age)
- Able to give informed consent
- AHI ≥ 5 on diagnostic night
- Either prescribed APAP, CPAP or Bi-level PAP for OSA
- Fluent in spoken and written English

Exclusion Criteria:

[figure not shown]
[figure not shown]
- Inability to give informed consent
- Participant intolerant to PAP
- Anatomical or physiological conditions making PAP therapy inappropriate
- Current diagnosis of respiratory disease or CO₂ retention
- Pregnant or may think they are pregnant.

[figure not shown]
8.9. Point of Enrolment

[figure not shown]
Participants will be recruited; who are prescribed either APAP, CPAP or Bi-level PAP for OSA at CTF. The principal investigator (or those identified in the delegation log) will ask the subjects whether they are interested to take part in the trial. The participants who meet the inclusion/exclusion criteria and provide informed consent will then be enrolled in to the trial. A recruitment script will be used when recruiting participants to the trial (Appendix A)

8.10. Participant Procedure

The study coordinator will ask the subjects whether they are interested to take part in the trial. Only eligible participants, that provide written informed consent, will be enrolled into the investigation.

[REDACTED]

REDACTED

REDACTED

REDACTED

REDACTED

REDACTED

8.11. Withdrawal Criteria

Participants will be informed that they have the right to withdraw from the study at any time, without prejudice to their medical care, and are not obliged to state their reasons. The participants is informed that they can revert back to their usual therapy during the clinical investigation if they have reason to do so. Additionally the investigator may withdraw a participant at any time for the following reasons:

- Protocol Violation
- Safety concerns
- Serious illness
- Adverse event

The reason for participant discontinuation in the study is to be recorded in the CRF and source document.

8.12. Number of Trial Subjects

A minimum number of 40-45 F&P full face mask users for OSA therapy will be recruited into this trial.

8.13. Follow up Plan

Participants will receive standard care from their health care provider throughout and following the study.

[REDACTED]

STATISTICAL CONSIDERATIONS

9.5. Description of the Statistical Design

Since the trial is to inform product development, no statistical design is required.

9.6. Sample Size

A minimum of 30 participants will be utilised for each investigation. According to the FDA guidance on Human Factors Engineering, a sample size of 30 will allow a mean of 99% of usability problems to be identified (minimum of 97%)⁷. This is deemed to be appropriate for this investigation as the product is

in feasibility, and the intent is to assess the usability of the user interface to determine further design iterations.

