9.10. Selection Criteria

All participants who consent, and are fitted with a mask that they attempt to sleep on will be included in the analysis. Please see section 8.10 for information on participant flow throughout the trial.

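### Does the minimum of 30 in section 9.6 need a stated problem frequency and a rule tying it to users of the New seal?

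*Combined protocol and SAP*

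**What the plan says.** Section 9.6 sets the size: "A minimum of 30 participants will be utilised for each investigation". The support is a figure from cited guidance, that "a sample size of 30 will allow a mean of 99% of usability problems to be identified (minimum of 97" per cent). The section regards this as suitable because the product is at the feasibility stage and "the intent is to assess the usability of the user interface to determine further design iterations". Section 9.5 adds that a study meant to inform product development needs no statistical design.

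Recruitment is set higher than 30. Section 7.3 says "Approximately 40-45 participants will be recruited for the trial by CTF", and 8.12 repeats the range.

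Four other sections bear on who contributes information about the New seal:

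- 8.2: "The Normal F&P mask seal (trial Seal B) will act as the control for this investigation".
- 8.3: "The order of the two masks issued to the participants will be randomized".
- 8.11: participants are told that "they have the right to withdraw from the study at any time".
- 9.10: those who consent and are "fitted with a mask that they attempt to sleep on will be included in the analysis". It then sends the reader to 8.10 for participant flow, and most of 8.10 is redacted in the public copy.

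**The concern.** Two things that any discovery share depends on are not fixed in the visible text.

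The first is frequency. Thirty users will almost surely show a problem that affects one user in five, but may well miss one that affects one in fifty. Section 9.6 does not say how common a problem must be for the study to be expected to find it. A clean result could then be read as 97% to 99% complete, when rarer problems may have gone unseen.

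The second is exposure. Read literally, 9.10 admits a participant who starts on Seal B, sleeps on it and withdraws before receiving the New seal. That person is analysed and, on one reading, counts towards the 30, yet cannot reveal a fault in the New seal. Discovery would then rest on fewer users than the stated minimum, and New-seal problem rates computed over everyone analysed would be too low. Since the study is meant to steer the next design iteration, a missed or understated problem is the relevant error.

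**Working it through.** **Inputs.** From the documents: minimum 30 (9.6); recruitment 40 to 45 (7.3, 8.12); cited share, mean 99% and minimum 97% (9.6). Assumed, because the visible text does not give them: independent users, problem frequency p, 1:1 allocation to order, and fraction d leaving before the second seal.

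**1. The plan's own figure.** It cannot be derived from the documents, because no p is given. If every problem had the same frequency, the chance of seeing it at least once among n users would be 1 − (1 − p)^n. Solving at n = 30:

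- 99%: p = 1 − 0.01^(1/30) = 0.142
- 97%: p = 1 − 0.03^(1/30) = 0.110

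Under that model the cited shares match problems affecting about 14% and 11% of users.

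**2. Discovery of one problem, 1 − (1 − p)^n.**

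| n | p = 10% | p = 5% | p = 2% |
|---|---|---|---|
| 30 | 95.8% | 78.5% | 45.5% |
| 40 | 98.5% | 87.1% | 55.4% |
| 45 | 99.1% | 90.1% | 59.7% |

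**3. Is this in conflict with 99%?** No. The cited figure is a share of all problems, so it averages over common and rare ones. As an illustration with an assumed mix, let 97% of problems affect 20% of users (each found with probability 1 − 0.80^30 = 0.9988) and 3% affect 5% of users (0.7854 each). The expected share found is 0.97 × 0.9988 + 0.03 × 0.7854 = 0.9688 + 0.0236 = 0.992. A mean above 99% and a 78.5% chance for a rarer problem can both be true.

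**4. Effect of early leavers.** Only control-first participants can be analysed without using the New seal, so New-seal users = n(1 − d/2). With d = 20%:

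- 30 analysed: 30 × 0.9 = 27 users; a 5% problem is found with 1 − 0.95^27 = 75.0% instead of 78.5%.
- 40 analysed: 40 × 0.9 = 36 users; 1 − 0.95^36 = 84.2% instead of 87.1%.

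**5. Loss needed to fall below 30 New-seal users.** This assumes that everyone else recruited uses the New seal.

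- 40 recruited: 40 − 29 = 11 losses among 20 control-first participants, or 55%.
- 45 recruited: 45 − 29 = 16 losses among about 22 (16/22.5 = 71%).

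**6. Denominator.** With 3 problems among 27 New-seal users in an analysed set of 30, the rate is 3/27 = 11.1% over users and 3/30 = 10.0% over everyone analysed, a gap of 1.1 percentage points. No visible section prescribes the second calculation.

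**The case for a change.** The best case for a change is that 9.6 makes a quantitative claim and rests the sample size on it, so the statement in 9.5 that no statistical design is needed does not excuse leaving out the assumption behind it. A problem seen in none of 30 users may still affect up to 1 − 0.05^(1/30) = 9.5% of them (one-sided 95% limit); for none of 40 the limit is 7.2% and for none of 45 it is 6.4%. A sentence on frequency and a denominator for each seal would cost little, and the denominator point does not depend on how many are recruited.

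Part of this stands. The visible text states no frequency, and anyone reading a clean result should keep those limits in mind. But adding a frequency would only record an assumption: the number recruited, the procedures and the data collected would stay the same. Exact intervals for each seal are good reporting practice, and the plan contradicts nothing by not listing them.

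The exposure half is weaker. Section 9.6 sets its 30 for the investigation, not for a seal, and 9.10 does not mention the 30, so linking them is the reader's inference. Because 9.10 defers to the redacted 8.10, this copy cannot show that an exposure or replacement rule is absent. Redefining the 30 as New-seal users would also matter only if losses were very heavy, and in that case it could require more participants.

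**Conclusion.** No change to the plan follows. The missing problem frequency is a real but minor gap: it limits what a reader can infer from the cited 99% and 97%, but it does not make those figures wrong, and followed as written the plan leads to no wrong result that can be shown from the documents. At the planned 40 to 45 users, a problem affecting 5% of users is found with probability 87.1% to 90.1%, a fair level for a feasibility study feeding further design work.

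The exposure point is one that analysts settle sensibly by counting each seal's problems among those who tried to sleep on it. At an assumed 20% loss before the second seal it costs about 3 percentage points of discovery probability for a 5% problem (87.1% to 84.2% with 40 analysed), and New-seal users stay at 30 or more unless over half of the control-first participants leave early.

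These sizes rest on independent users, 1:1 order, everyone else recruited using the New seal, and assumed values of p and d. The redacted participant flow in 8.10 could make the exposure point smaller still.

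### Does the usability-based rationale for 30 participants in Section 9.6 leave the treatment part of the primary outcomes in Section 8.4.1 without a valid sample size?

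*Combined protocol and SAP*

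**What the plan says.** Section 9.6 sets the number: "A minimum of 30 participants will be utilised for each investigation". Its one numerical support is a figure cited from guidance: "a sample size of 30 will allow a mean of 99% of usability problems to be identified (minimum of 97"%). It calls this suitable because the product is at the feasibility stage and "the intent is to assess the usability of the user interface to determine further design iterations".

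Section 8.4.1 lists two primary outcomes. The first is comfort: "The F&P mask seal is comfortable to use for the participant as measured by the custom questionnaires and recorded during the interviews". The second has three parts: ease of use, acceptance by the participant, and that the mask "provides adequate treatment for OSA during in-home use, measured via participant feedback and PAP data download (if applicable"). Section 6.5 says that efficacy data from the CPAP download are collected "to ensure the study mask provides effective treatment and performs as participants stand care".

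Four other sections bear on the point:

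- Section 7.2 frames the primary objective around the participant's own view of comfort, experience and satisfaction.
- Section 8.4.2 makes leak and PAP data a secondary outcome.
- Section 9.5 holds that a trial meant to inform product development needs no statistical design.
- Sections 7.3 and 8.12 plan to recruit 40 to 45 participants.

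**The concern.** Section 9.6 passes from the usability yield to a general statement of suitability: "This is deemed to be appropriate for this investigation as the product is" in feasibility. That reads as cover for the whole investigation, while the primary outcomes reach further than usability. A problem-discovery yield is the chance of meeting a problem at least once. It gives no precision for a proportion of users adequately treated, for a mean AHI or leak, or for a difference between the two seals.

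The download is also collected only where applicable, so the number with PAP data could fall below 30. The risk would be a report that concludes the mask treats OSA adequately and points to Section 9.6 for its sample size. The 97% to 99% would then lend that conclusion an assurance that 30 participants do not supply.

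**Working it through.** **1. The plan's own figure.** Inputs from Section 9.6: n = 30, mean 99%, minimum 97%. The documents give no per-participant detection probability p, so the figure is cited and cannot be derived from their inputs. Under the simple discovery model (an assumption here), yield = 1 − (1 − p)^30. Solving backwards:

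- 99%: p = 1 − 0.01^(1/30) = 0.142
- 97%: p = 1 − 0.03^(1/30) = 0.110

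Over an assumed range of p from 0.05 to 0.31, the yield at n = 30 runs from 78.5% to about 100%. Nothing here contradicts the cited figure.

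**2. What the numbers give for treatment adequacy.** No definition or threshold is readable, so a yes/no measure is assumed. With no failures among n participants, the one-sided 95% upper limit on the inadequate rate is 1 − 0.05^(1/n). The exact two-sided 95% lower limit for n of n adequately treated is 0.025^(1/n). If the true inadequate rate is 5%, the chance of seeing none is 0.95^n.

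| n | Upper limit, no failures | Lower limit, n of n | Chance of none at a 5% rate |
|---|---|---|---|
| 30 | 9.5% | 88.4% | 21.5% |
| 40 | 7.2% | 91.2% | 12.9% |
| 45 | 6.4% | 92.1% | 9.9% |

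If only 20 participants had downloads (assumed), the upper limit would be 13.9%; with 15 it would be 18.1%. With failures, 27 of 30 has an exact 95% interval of 73.5% to 97.9%.

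**3. If the measure were continuous.** The 95% half-width for a paired mean difference is t/√n in units of the SD of the within-participant difference: 0.37 SD at n = 30, 0.32 at 40 and 0.30 at 45.

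**4. Is there a target to miss?** Showing that 30 is too few needs a margin, a threshold, or a rate to exclude. The readable text gives none. With no failures, excluding a 5% rate takes ln 0.05 / ln 0.95, rounded up to 59, and excluding 3% takes 99. Both rates are the reviewer's choice, not the plan's. Sections 7.1, 8.5, 8.6 and 9.7 show headings only, Section 8.10 is largely redacted, and a redacted block precedes the statistical section, whose readable numbering starts at 9.5. A criterion may stand in any of these.

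**5. Does Section 9.6 claim more than it should?** The noun in the cited sentence is usability problems, and the reason that follows is the usability of the user interface. No readable section applies the yield to treatment. Section 9.5 declines formal inference, and Section 9.8 says that statistical outcomes will not alter how the study is run.

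**6. Would a change to the plan alter a result?** A caveat in Section 9.6 would alter none. Reporting adequacy only among those with PAP data would drop the participant feedback that Section 8.4.1 names as a measure. It would also depart from Section 9.10, which analyses everyone fitted with a mask they tried to sleep on. Writing detection probabilities into Section 9.6 would add a model that the documents do not use.

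**The case for a change.** The strongest case for a change is that adequate treatment is named as primary and Section 6.5 confirms that it is a real aim. Feasibility justifies a small sample, but it does not make a usability yield apply to treatment. Waiving a statistical design does not remove the need for a denominator and an interval, and Section 9.9 itself refers to a statistical plan. A sentence of clarification would cost almost nothing.

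Part of this stands. The intent stated in Section 9.6 is narrower than Section 8.4.1, and no readable text gives a precision basis for the treatment part. The limits in the working are correct under their assumptions, and a report should not present 97% to 99% as evidence about treatment.

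The step from there to a defect does not stand. The misuse is hypothetical, since Section 9.6 names what its figure covers. Treatment adequacy is one of three parts of one outcome, is judged partly by participant feedback, and sits under an objective about participants' views. A feasibility study may be sized on its main purpose and describe the rest. Stating how many participants had PAP data, and giving an interval where the measure allows one, is routine reporting that an analyst would supply without an amendment.

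**Conclusion.** No change follows. The rationale in Section 9.6 covers usability only, while Section 8.4.1 also names treatment adequacy, so the scopes differ; but no stated figure is wrong and no stated target is missed. Following the plan as written does not lead to a demonstrated wrong result.

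The size of the point is the uncertainty that any trial of this size carries: an upper limit of 9.5% on inadequate treatment at 30 participants with no failures, or 7.2% to 6.4% at the planned 40 to 45. It would be wider if fewer had downloads. These values assume a yes/no measure and no failures. The number with downloads is not known, and the criterion for adequacy is not readable. The conclusion also rests on treatment data being used descriptively, as Section 9.5 implies. If unseen text set a formal treatment criterion, the sample size would have to be judged against that criterion.
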